7.1.1.2.6 Blood and Urine Collection for Laboratory Evaluations

In addition to screening evaluations (see [Section 7.1.1.1.6](#)), subjects will have blood and urine specimens collected for clinical evaluation (see [Section 7.2.1 Clinical Laboratory Evaluations](#)). Refer to [Section 15 Schedule of Events](#) for timing and frequency of blood and urine collection for laboratory evaluations.

The following labs will be performed within ~48 hours after the end of the infusion on Day 3 (exit lab panel):

- Infectious serology (anti-HIV antibodies, anti-hepatitis B surface antigen, anti-hepatitis B core antigen, anti-hepatitis C antibodies), direct antiglobulin test, RBC antibody screen (including direct Coombs and anti-RBC antibody).
- ALT, AST, bilirubin (total), ionized calcium, chloride, creatinine, potassium, protein total, sodium, blood urea nitrogen, PTT, PT/INR.
- CBC with differential (basophils, eosinophils, lymphocytes, monocytes, neutrophils).
- Urinalysis: blood, glucose, ketone, protein, pH, specific gravity, nitrite, leukocytes, urine creatinine, urine protein, urine protein/creatinine ratio, and reflex urine microscopy if indicated.
- Pregnancy test.

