7.3.4 BASELINE: ON-SITE/TREATMENT

The on-site Baseline assessments will be gathered prior to the first infusion on Day 1. After the first infusion on Day 1, the subject will be discharged from the facility and come back the following morning (Day 2) for the inpatient period. The inpatient treatment period is 2 days during which each subject will receive 3 additional doses of 250 mL of their assigned treatment allocation (i.e., either GRF6021 or placebo).

Visits 3 through 5, Treatment (Days 1-3):

- Perform the following procedures on each day *prior* to administering (the first) study infusion:
 - Review AEs and concomitant medications.
 - 12-lead ECG (**Day 1 and 3 Only**).
 - Collect sample for CyTOF assessment (**Including second infusion on Day 2**).

- Obtain samples for proteomic assessments; fasting samples preferred (**Including second infusion on Day 2**).
- Collect vital signs (BP, HR, RR, and body temperature) (**Including second infusion on Day 2**).
- Targeted physical exam (**Day 1 and 3 Only**).
- Pregnancy testing for WOCBP (**Day 1 Only**).
- Administer 3D-CAM, SRS, and WOMAC (**Day 1 and 3 Only**).
- ActiGraph device data collection (**Day 1 and 3 Only**).
- Administer study treatment per the GRF6021 Infusion Administration Manual:
 - On the day before surgery (**Day 1**).
 - On the day of surgery within 4 hours before surgery start (first incision) (**Day 2**).
 - On the day of surgery upon arrival in the PACU (within 5 hours after the first incision) (**Day 2**).
 - On the day after surgery (**Day 3**).
- Perform the following assessments following each infusion start:
 - BP and HR at 15, 30, 45, and 60 min after infusion start.
 - Body temperature and RR at 60 minutes.
 - Collection of perioperative data (**Day 2 Only**, after second infusion).
 - Opioid consumption assessment (**Days 2 and 3 Only**).
 - 12-lead ECG (**Day 3+1 Only**, after end of last infusion).
 - Exit lab panel including pregnancy test (**Day 3 Only**, after end of last infusion).
 - Administer 3D-CAM (**Day 2 Only**, after second infusion).

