7.3.5 FOLLOW-UP

All Follow-up Visits will be conducted remotely by phone or electronically.

Visits 6 through 14 (Day 4 through Day 37±2)

- Review AEs and concomitant medications.
- Perform the following assessments:
 - SRS
 - WOMAC
 - Opioid consumption assessment.
- Review AEs and concomitant medications.
- Ongoing collections of data from wearable device.

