	X ² : To be performed: Prior to each infusion, within 1 hour of infusion start: BP, HR, RR, and body temperature. After the start of each infusion, at 15, 30, and 45 minutes: BP and HR. At 60 minutes after infusion start: BP, HR, RR, and body temperature.
	X ³ : To be performed following final infusion on Day 3.
	a: Preoperative infusion on the day of surgery.
	b: Postoperative infusion on the day of surgery.
	c: Screening lab panel: Alkaline phosphatase, ALT, AST, bicarbonate, bilirubin (total), ionized calcium, chloride, creatinine, GGT, glucose (random), lactate dehydrogenase, magnesium, phosphate, potassium, protein total, sodium, blood urea nitrogen, albumin, PTT, PT/INR. CBC with differential (basophils, eosinophils, lymphocytes, monocytes, neutrophils). Urinalysis: blood, glucose, ketone, protein, pH, specific gravity, nitrite, leukocytes, urine creatinine, urine protein/creatinine ratio, (and reflex urine microscopy if indicated). Infectious serology (anti-HIV antibodies, anti-hepatitis B surface antigen, anti-hepatitis B core antigen, anti-hepatitis C antibodies), direct antiglobulin test, RBC antibody screen (including direct Coombs and anti-RBC antibody), serum IgA, and haptoglobin. Urine drug screen: cannabinoids, benzodiazepine, barbiturates, opiates, cocaine, amphetamines, phencyclidine.
	d: Exit lab panel performed within ~48 hours after the last infusion (Day 3): Infectious serology (anti-HIV antibodies, anti-hepatitis B surface antigen, anti-hepatitis B core antigen, anti-hepatitis C antibodies), direct antiglobulin test, RBC antibody screen (including direct Coombs and anti-RBC antibody), ALT, AST, bilirubin (total), ionized calcium, chloride, creatinine, potassium, protein total, sodium, blood urea nitrogen, PTT, PT/INR. CBC with differential (basophils, eosinophils, lymphocytes, monocytes, neutrophils). Urinalysis: blood, glucose, ketone, protein, pH, specific gravity, nitrite, leukocytes, urine creatinine, urine protein, urine protein/creatinine ratio, and reflex urine microscopy if indicated.
	e: Serum pregnancy test required at screening. Serum and/or urine pregnancy test may be used at subsequent timepoints.
	f: For proteomic assessments, fasting samples are preferred.
	g: Baseline opioid consumption assessment will be included at screening during medication history. Subsequent opioid measurements will begin following surgery on Day 2 (Visit 4b).

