	h: The ActiGraph wearable device will be given to the subject at the screening visit. Between -7 and -3 days before surgery, the subject will be told by phone to put the ActiGraph on and wear it until admission. The ActiGraph will be removed for the surgery on Day 2 (Visits 4a and 4b).
	i: On Day 3, second 12-lead ECG to be performed within +1 day

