8.2 Study Populations for Analysis

- Evaluable set: Subjects who received all 4 doses and in whom all blood samples were collected.
- Per Protocol set (PP): A subset of evaluable subjects who have completed all 4 doses of treatment and evaluations through Visit 5 and who follow the protocol without any major deviation(s). A subject who received Decadron will be excluded.

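### The exit lab panel is given two different timings, and both its window and that of the final ECG run past the last scheduled on-site visit

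*Protocol*

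**What the plan says.** **Exit lab panel.** Protocol 7.3.4 lists "Exit lab panel including pregnancy test (Day 3 Only, after end of last infusion". Protocol 7.1.1.2.6 says "The following labs will be performed within ~48 hours after the end of the infusion on Day 3 (exit lab panel". Footnote d to the schedule in Protocol 15.1 says "Exit lab panel performed within ~48 hours after the last infusion (Day 3". The schedule places the panel in the Visit 5 (Day 3) column.

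**ECG after the last infusion.** Protocol 7.3.4 gives Day 3 plus one day. Footnote i in 15.1 says "On Day 3, second 12-lead ECG to be performed within +1 day". A separate ECG is listed before the infusion on Day 1 and again before the infusion on Day 3.

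**On-site period.** Under Protocol 7.3.4 "The inpatient treatment period is 2 days", that is, Days 2 and 3. Protocol 7.3.5, which starts with Visit 6 on Day 4, states "All Follow-up Visits will be conducted remotely by phone or electronically". Section 7.3.6 makes the End of Study visit remote as well. Section 7.3.7 asks for the exit panel at early termination only if the subject is still at the site.

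**Endpoints that use these data.** Protocol 4.2.2 lists change from baseline in laboratory parameters and in ECG as secondary endpoints. Time to discharge is a secondary endpoint in its own right.

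**Analysis set.** SAP 8.2 defines the Evaluable set as subjects who had all four doses and "in whom all blood samples were collected". Protocol 5.4.2, Protocol 10.1 and SAP 7.3 limit that condition to the draws needed for the primary endpoint.

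**The concern.** Two things need attention. First, the site has two rules for one procedure, so whether a Day 4 or Day 5 draw counts as a protocol deviation depends on which section is read.

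Second, both windows stay open after the last visit at which blood can be drawn or an ECG recorded under the schedule. A subject can leave hospital on Day 3 with either procedure still inside its window, and so be compliant at that moment, yet have no later scheduled on-site contact.

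The exit panel is the only scheduled clinical chemistry and blood count after dosing. It therefore carries the laboratory endpoint, and it is the only scheduled post-dose creatinine for the reduced-kidney-function event of special interest in Protocol 8.4.3. If panels were missed mainly in subjects who went home early, the missing data would be related to speed of recovery, which the trial is studying.

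**Working it through.** The plan states no figure to reproduce. The check sets the passages side by side and does calendar arithmetic.

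**1. Do the timings agree?**

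| Procedure | Section 7.3.4 | Section 7.1.1.2.6 | Section 15.1 | Agree? |
|---|---|---|---|---|
| Exit lab panel | Day 3 | about 48 h after infusion 4 | about 48 h after infusion 4 (footnote d) | No |
| ECG after last infusion | Day 3 + 1 day | not stated | within +1 day (footnote i) | Yes |

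Only the laboratory passages conflict.

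**2. Where do the windows end?**

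- Labs: end of infusion on Day 3 + 48 h = Day 5.
- ECG: Day 3 + 1 = Day 4.
- Last scheduled on-site visit: Visit 5, Day 3. First remote visit: Visit 6, Day 4.

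The lab window runs two study days past the last scheduled on-site day, and the ECG window one day past it.

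**3. How much of the lab window falls on Day 3?** The documents give no clock time for infusion 4. Assume a start between 07:00 and 18:00 and the stated duration of about 30 minutes (0.5 h).

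- Start 07:00: 24 − 7 − 0.5 = 16.5 h on Day 3; 16.5/48 = 34%.
- Start 18:00: 24 − 18 − 0.5 = 5.5 h on Day 3; 5.5/48 = 11%.

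Under that assumption, roughly two thirds to nine tenths of the window lies after Day 3. This describes the window and does not predict how many draws are missed.

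**4. What backup is scheduled?**

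- Clinical lab panels: one at screening and one at exit, so one after dosing.
- ECGs after at least one infusion: two. The Day 3 pre-infusion ECG follows 1 (Day 1) + 2 (Day 2) = 3 of the 4 infusions. The second Day 3 ECG follows all 4.

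A missed exit panel leaves no scheduled post-dose safety labs. A missed final ECG leaves the ECG taken after three infusions, but none after the fourth.

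**5. Is either procedure tied to discharge?** No passage requires completion before the subject leaves, and no on-site return is scheduled. The early-termination text recognises presence at the site as the limit, but it covers early terminators only.

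**The case against.** The strongest reply is that this is an editing slip with no demonstrated loss. In Section 7.3.4 the Day 3 tag sits in a list covering several treatment days, so it may say which infusion day the panel belongs to and not how wide the window is. The revision history for Version 3.0 records that the 48-hour window was added to 7.1.1.2.6 for feasibility, which suggests that the change was not carried through. A limit of this kind also permits a draw straight after infusion 4, and the schedule assigns the panel to an on-site visit. The two-day inpatient treatment period does not fix the day of discharge, and nothing forbids a return draw.

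Most of this stands. It shows that loss is possible but not built in. It does not remove the conflict: the neighbouring ECG line in 7.3.4 does carry its extra day, so a reader would take the absence of one on the lab line as deliberate. Nor does it supply an on-site contact for the later part of either window.

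Two stronger readings are tempting, and the documents do not support them.

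- A reader might infer that a missed exit panel removes a subject from the mass cytometry analysis, because SAP 8.2 asks for all blood samples. Protocol 5.4.2, Protocol 10.1 and SAP 7.3 all restrict the requirement to the primary-endpoint draws, and the exit panel is not one of them. What remains is a looser wording in SAP 8.2.
- A reader might infer that an early-discharged subject loses every post-dose ECG. The Day 3 pre-infusion ECG follows three infusions, so only the ECG after the final infusion is at risk.

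**Conclusion.** The point holds and is minor. One section conflicts with two others on when the exit panel is due. Both the lab window (to Day 5) and the consistently stated ECG window (to Day 4) extend past the last scheduled on-site visit on Day 3. A subject discharged that day could miss the only scheduled post-dose safety labs and the only scheduled ECG after infusion 4.

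The size of any loss cannot be computed, because the documents give no discharge times and do not say when in the window the procedures were done. A reader might divide one subject by half of the 37 evaluable subjects in SAP 7.3 and quote about 5% of an arm per missed panel (1/19 = 5.3%, 1/18 = 5.6%). That is the wrong denominator: Protocol 10.3 puts safety analyses on everyone who received at least one dose, and neither that number nor its split by arm is given. A link between missingness and recovery is plausible because time to discharge is an endpoint, but it is not shown.

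The supplied SAP covers only the high-dimensional endpoints. Laboratory and ECG analyses are in a separate SAP dated 08OCT2020, so how that document treats windows and missing panels cannot be judged here. The secondary endpoints are descriptive and unpowered (Protocol 4.2.2), which also limits the consequence.

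**What to change.** - Reconcile Protocol 7.1.1.2.6, 7.3.4 and footnotes d and i of 15.1 with each other and with the on-site period, so that each window is covered by an on-site contact for every subject. How to do this is for the sponsor to choose; completion before discharge and a stated provision for a return draw are two ways of closing the gap.
- Record the actual time of the exit draw and of the final ECG. State how a Day 4 or Day 5 draw is classified.
- Report missing exit panels by arm in the Safety Dataset. SAP 7.3 says that enrollment has ended, so this reporting step is now the most useful part. It belongs in the analysis plan or study report that covers the laboratory endpoint.
- In SAP 8.2, replace the general reference to blood samples with the SAP 7.3 condition that limits it to draws for the primary endpoint.

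The cost is a few lines of wording and one short table. If the sponsor chooses completion before discharge, some draws will come earlier in the window. If it chooses a return draw, some subjects will have an extra trip. No new test is needed in either case.

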17 APPENDICES

The assessments in this section and associated information are provided as EXAMPLES ONLY. The actual assessments, related source documents, and instructions for administration and scoring are included in the associated guides if available.

Appendix 1. 3-Minute Diagnostic Interview for Confusion Assessment Method

The 3D-CAM (Inouye 2003) is a brief verbal assessment tool used to test patients for delirium. Each item in the instrument directly informs one of the 4 CAM features. For all items, the patient's answer is "incorrect" or "yes."

3D CAM ASSESSMENT		CAM Feature					
Coding Instructions: Incorrect also includes "I don't know", and No response/non-sensical responses. For any 'Incorrect' or 'Yes' responses, check the box in the final column designating which feature is present.		1	2	3	4		
READ: I have some questions about your thinking and memory....		 Incorrect	 Correct				
1. Can you tell me the year we are in right now?		 Incorrect	 Correct				
2. Can you tell me the day of the week?		 Incorrect	 Correct				
3. Can you tell me what type of place is this? [hospital]		 Incorrect	 Correct				
4. I am going to read some numbers. I want you to repeat them in backwards order from the way I read them to you. For instance, if I say "5 – 2", you would say "2 -5". OK? The first one is "8-2-5" (5-2-8).		 Incorrect	 Correct				
5. The second is "3-1-9-4" (4-9-1-3).		 Incorrect	 Correct				
6. Can you tell me the days of the week backwards, starting with Saturday? [S,F,T,W,T,M,S] may prompt with "what is day before" for up to 2 prompts.		 Incorrect	 Correct				
7. Can you tell me the months of the year backwards, starting with December? [D,N,O,S,A,J,J,M,A,M,F,J] may prompt with "what is month before" for up to 2 prompts.		 Incorrect	 Correct				
8. During the past day have you felt confused?		 Yes	 No				
9. [IF Q3 is "Incorrect", do not ask and check "Yes", otherwise, ASK] During the past day did you think that you were not really in the hospital?		 Yes	 No				
10. During the past day did you see things that were not really there?		 Yes	 No				
Observer Ratings: To be completed after asking the patient questions 1-10 above.							
11. Was the patient sleepy, stuporous, or comatose during the interview?		 Yes	 No				
12. Did the patient show excessive absorption with ordinary objects in the environment (hypervigilant)?		 Yes	 No				
13. Was the patient's flow of ideas unclear or illogical, for example tell a story unrelated to the interview (tangential)?		 Yes	 No				
14. Was the patient's conversation rambling, for example did he/she give inappropriately verbose and off target responses?		 Yes	 No				
15. Was the patient's speech unusually limited or sparse? (e.g. yes/no answers)		 Yes	 No				
16. Did the patient have trouble keeping track of what was being said during the interview?		 Yes	 No				
17. Did the patient appear inappropriately distracted by environmental stimuli?		 Yes	 No				
18. Did the patient's level of consciousness fluctuate during the interview, for example, start to respond appropriately and then drift off?		 Yes	 No				
19. Did the patient's level of attention fluctuate during the interview, e.g., did the patient's focus on the interview or performance on the attention tasks vary significantly?		 Yes	 No				
20. Did the patient's speech/thinking fluctuate during the interview, for example, patient spoke slowly, then spoke very fast?		 Yes	 No				
OPTIONAL QUESTIONS: COMPLETE ONLY IF FEATURE 1 IS NOT CHECKED AND FEATURE 2 IS CHECKED AND EITHER FEATURE 3 OR 4 IS CHECKED							
21. Contact a family member, friend, or health care provider who knows the patient well and ask: "Is there evidence of an acute change in mental status (memory or thinking) from the patient's baseline?"		 Yes	 No				
22. IF SECOND DAY OF HOSPITALIZATION OR LATER AND PREVIOUS 3D-CAM RATINGS ARE AVAILABLE: Review previous 3D-CAM assessments and determine if there has been an acute change in performance, based on ANY new "positive" items		 Yes	 No				
CAM Summary: Check if Feature Present in column above				1	2	3	4
DELIRIUM REQUIRES FEATURE 1 AND 2 and EITHER 3 OR 4: _____ Present _____ Not Present							

Appendix 2. Surgery Recovery Scale

The SRS ([Paddison 2011](#)) is a sensitive and simple tool for the assessment of functional recovery following major surgery. The scale contains 13 items. Impacts on daily activities are scored from 1 to 5 (1= not at all). It's considered the most broadly validated measure of surgical recovery available.

Surgery Recovery Scale

During the last two days:

- I have been feeling energetic
- I have been feeling worn out
- I have been feeling vigorous
- I have been forgetful
- I have achieved very little with the day
- I have been feeling fatigued
- Physically, I have felt tired
- I have had to restrict how much I try to do in a day
- I have been feeling lively

During the last two days, I have had enough energy to:

- Read a newspaper/book or watch TV
- Dress
- Do household chores
- Engage in leisure or recreational activities
- Shop or do errands

Appendix 3. Western Ontario and McMaster Universities Osteoarthritis Index

The WOMAC ([Bellamy 1986, Bellamy 2002](#)) was developed to assess pain, stiffness, and physical function in patients with knee and/or hip osteoarthritis, but it has been used among patients with many different conditions. The WOMAC is one of the most widely utilized self-report measures of lower extremity symptoms and function. It has been studied over a period of almost 30 years in many different contexts and patient populations, and there are abundant data regarding its utility and measurement properties. The Likert Scale version uses an 11-point scale anchored by “no pain” and “extreme pain” for pain, and “no difficulty” and “extreme difficulty” for physical function. Higher scores on the WOMAC indicate worse pain and functional limitations.

Appendix 4. Short Form-36

The SF-36 (Laucis 2015) is the most widely used health-related quality-of-life measure in research to date. The SF-36 yields 8 scale scores and 2 summary scores. The physical component summary and mental component summary scores.

SF-36 QUESTIONNAIRE			
Name: _____	Ref. Dr: _____	Date: _____	
ID#: _____	Age: _____	Gender: M / F	
Please answer the 36 questions of the Health Survey completely, honestly, and without interruptions.			
GENERAL HEALTH:			
In general, would you say your health is: 
  Excellent  Very Good  Good  Fair  Poor 
			
Compared to one year ago, how would you rate your health in general now? 
  Much better now than one year ago  Somewhat better now than one year ago  About the same  Somewhat worse now than one year ago  Much worse than one year ago 
			
LIMITATIONS OF ACTIVITIES: The following items are about activities you might do during a typical day. Does your health now limit you in these activities? If so, how much?			
Vigorous activities, such as running, lifting heavy objects, participating in strenuous sports. 
  Yes, Limited a lot  Yes, Limited a Little  No, Not Limited at all 
			
Moderate activities, such as moving a table, pushing a vacuum cleaner, bowling, or playing golf 
  Yes, Limited a Lot  Yes, Limited a Little  No, Not Limited at all 
			
Lifting or carrying groceries 
  Yes, Limited a Lot  Yes, Limited a Little  No, Not Limited at all 
			
Climbing several flights of stairs 
  Yes, Limited a Lot  Yes, Limited a Little  No, Not Limited at all 
			
Climbing one flight of stairs 
  Yes, Limited a Lot  Yes, Limited a Little  No, Not Limited at all 
			
Bending, kneeling, or stooping 
  Yes, Limited a Lot  Yes, Limited a Little  No, Not Limited at all 
			
Walking more than a mile 
  Yes, Limited a Lot  Yes, Limited a Little  No, Not Limited at all 
			
Walking several blocks 
  Yes, Limited a Lot  Yes, Limited a Little  No, Not Limited at all 
			
Walking one block 
  Yes, Limited a Lot  Yes, Limited a Little  No, Not Limited at all 
			

Appendix 5. Beck Depression Inventory-II

The BDI-II (Beck 1996) is a 21-item self-administered survey is scored on a scale of 0–3 in a list of four statements arranged in increasing severity about a particular symptom of depression.

 Beck Depression Inventory		Baseline	
V 0477	CRTN: _____	CRF number: _____	Page 14 patient initis: _____
			
Date: _____			
Name: _____ Marital Status: _____ Age: _____ Sex: _____ Occupation: _____ Education: _____			

Instructions: This questionnaire consists of 21 groups of statements. Please read each group of statements carefully, and then pick out the one statement in each group that best describes the way you have been feeling during the past two weeks, including today. Circle the number beside the statement you have picked. If several statements in the group seem to apply equally well, circle the highest number for that group. Be sure that you do not choose more than one statement for any group, including Item 16 (Changes in Sleeping Pattern) or Item 18 (Changes in Appetite).
			
1. Sadness 0 I do not feel sad. 1 I feel sad much of the time. 2 I am sad all the time. 3 I am so sad or unhappy that I can't stand it.		6. Punishment Feelings 0 I don't feel I am being punished. 1 I feel I may be punished. 2 I expect to be punished. 3 I feel I am being punished.	
2. Pessimism 0 I am not discouraged about my future. 1 I feel more discouraged about my future than I used to be. 2 I do not expect things to work out for me. 3 I feel my future is hopeless and will only get worse.		7. Self-Dislike 0 I feel the same about myself as ever. 1 I have lost confidence in myself. 2 I am disappointed in myself. 3 I dislike myself.	
3. Past Failure 0 I do not feel like a failure. 1 I have failed more than I should have. 2 As I look back, I see a lot of failures. 3 I feel I am a total failure as a person.		8. Self-Criticalness 0 I don't criticize or blame myself more than usual. 1 I am more critical of myself than I used to be. 2 I criticize myself for all of my faults. 3 I blame myself for everything bad that happens.	
4. Loss of Pleasure 0 I get as much pleasure as I ever did from the things I enjoy. 1 I don't enjoy things as much as I used to. 2 I get very little pleasure from the things I used to enjoy. 3 I can't get any pleasure from the things I used to enjoy.		9. Suicidal Thoughts or Wishes 0 I don't have any thoughts of killing myself. 1 I have thoughts of killing myself, but I would not carry them out. 2 I would like to kill myself. 3 I would kill myself if I had the chance.	
5. Guilty Feelings 0 I don't feel particularly guilty. 1 I feel guilty over many things I have done or should have done. 2 I feel quite guilty most of the time. 3 I feel guilty all of the time.		10. Crying 0 I don't cry anymore than I used to. 1 I cry more than I used to. 2 I cry over every little thing. 3 I feel like crying, but I can't.	
 THE PSYCHOLOGICAL CORPORATION® Harcourt, Brace & Company SAN ANTONIO		Subtotal Page 1 Continued on Back <small>Orlando • Boston • New York • Chicago • San Francisco • Atlanta • Dallas San Diego • Philadelphia • Austin • Fort Worth • Tennessee • London • Sydney</small> <small>Copyright © 1996 by Aaron T. Beck All rights reserved. Printed in the United States of America.</small>	
		0154018392 NR15645	

 Beck Depression Inventory V 0477		Baseline	
		CRTN: _____	CRF number: _____
11. Agitation 0 I am no more restless or wound up than usual. 1 I feel more restless or wound up than usual. 2 I am so restless or agitated that it's hard to stay still. 3 I am so restless or agitated that I have to keep moving or doing something.		17. Irritability 0 I am no more irritable than usual. 1 I am more irritable than usual. 2 I am much more irritable than usual. 3 I am irritable all the time.	
12. Loss of Interest 0 I have not lost interest in other people or activities. 1 I am less interested in other people or things than before. 2 I have lost most of my interest in other people or things. 3 It's hard to get interested in anything.		18. Changes in Appetite 0 I have not experienced any change in my appetite. 1a My appetite is somewhat less than usual. 1b My appetite is somewhat greater than usual. 2a My appetite is much less than before. 2b My appetite is much greater than usual. 3a I have no appetite at all. 3b I crave food all the time.	
13. Indecisiveness 0 I make decisions about as well as ever. 1 I find it more difficult to make decisions than usual. 2 I have much greater difficulty in making decisions than I used to. 3 I have trouble making any decisions.		19. Concentration Difficulty 0 I can concentrate as well as ever. 1 I can't concentrate as well as usual. 2 It's hard to keep my mind on anything for very long. 3 I find I can't concentrate on anything.	
14. Worthlessness 0 I do not feel I am worthless. 1 I don't consider myself as worthwhile and useful as I used to. 2 I feel more worthless as compared to other people. 3 I feel utterly worthless.		20. Tiredness or Fatigue 0 I am no more tired or fatigued than usual. 1 I get more tired or fatigued more easily than usual. 2 I am too tired or fatigued to do a lot of the things I used to do. 3 I am too tired or fatigued to do most of the things I used to do.	
15. Loss of Energy 0 I have as much energy as ever. 1 I have less energy than I used to have. 2 I don't have enough energy to do very much. 3 I don't have enough energy to do anything.		21. Loss of Interest in Sex 0 I have not noticed any recent change in my interest in sex. 1 I am less interested in sex than I used to be. 2 I am much less interested in sex now. 3 I have lost interest in sex completely.	
16. Changes in Sleeping Pattern 0 I have not experienced any change in my sleeping pattern. 1a I sleep somewhat more than usual. 1b I sleep somewhat less than usual. 2a I sleep a lot more than usual. 2b I sleep a lot less than usual. 3a I sleep most of the day. 3b I wake up 1-2 hours early and can't get back to sleep.		Subtotal Page 2 Subtotal Page 1 Total Score	
		NR15645	

3456789101112 ABCDE

